Pain Neuroscience Education (PNE) is a technique that shifts the focus from the diseased knee joint and the assumption that pain stems from degenerative structural changes [14]. Unlike standard OA education that has historically had a biomedical influence [14], PNE reconceptualizes pain as a danger signal and introduces intrinsic modulation of pain to influence the pain experience. Omitting biomedical language from KOA education can lead to significantly lower perceptions that physical activity is injurious to the knee joint, lower fear of movement, and improve participation in exercise [14]. Combined with active treatment strategies such as exercise, PNE results in positive changes in pain [15].

The need for high quality research that evaluates the effects of mind- body approaches in managing KOA pain and understanding how they may modify altered nervous system processing is needed. Our group has developed a program we call Pain Informed

Movement, which is a combination of neuromuscular exercise, mind-body techniques, and PNE with the aim of improving intrinsic pain modulation in people with KOA. Although each of these components as a standalone technique can improve pain in KOA, their cumulative effect may be more substantial and has the potential to lead to an enhancement of outcomes, as each component can lead to optimization of the other. Given that the feasibility and acceptability of the Pain Informed Movement program has been previously established [16], further evaluation of this program compared to standard care is warranted. This paper presents a detailed protocol for a pilot randomized controlled trial (RCT) to collect pilot data, as well as initial efficacy data on the comparison of Pain Informed Movement program with neuromuscular exercise and standard OA education in people with KOA. This study has been approved by the Hamilton Integrated Research Ethics Board and registered on clinicaltrials.gov (ID: NCT05730829).

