## **2.2. Study participants**

Sample size is based on the primary outcome of complete follow-up using the confidence interval method for calculating sample size in pilot trials [20]. We will aim for 90% follow-up but will consider the trial successful if we achieve 81%. To achieve a margin of error of 9%, with 10% added for attrition, we will require 66 participants (n ¼ 33 per arm).

Participants will be recruited through the email lists of the McMaster University's community and research centers and their social media pages. Additionally, the study poster will be placed on other social media channels (e.g., Twitter, Facebook advertisements) and flyers will be placed in local Orthopaedic surgeon, Rheumatologist, and Psychiatrists offices.

The inclusion and exclusion criteria are listed in Table 1.

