**Table 1**  
Inclusion and exclusion criteria.

Inclusion criteria	Exclusion criteria

≥40 years of age with diagnosis of knee osteoarthritis (KOA by) a physician
 
OR ≥45 years of age and having
 
activity-related knee joint pain with or without morning stiffness lasting ≤30 min (NICE criteria)
 
2 Having an average pain intensity of at least 3/10 on a numeric pain scale on most days of the past month
	
1 Cannot communicate in English
 
3 Has inflammatory arthritis or other systemic conditions
 
4 Has had lower limb trauma or surgery within the past 6 months
 
5 Has participated in a KOA exercise program in the past 3 months
 
1 Has had any injection in the index knee within 3-months prior to baseline assessment
 
2 Does not have regular access to the internet
 
3 Inability to get up and down from the floor independently
 
4 Use of mobility aids
 
5 Currently participating in any other drug/device/exercise clinical trial related to OA
 
6 Planned absences (e.g., trips away) of >1 week
 
7 Currently receiving other forms of care for KOA pain (e.g., from a physiotherapist, chiropractor, athletic therapist, kinesiologist)
 
8 Does not meet screening for safe participation in exercise according to the Get Active questionnaire from the Canadian Society for Exercise Physiology [25]

[figure not shown]

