### 2.3. Screening and assessments

Potential participants will contact the research team through the contact information provided in the flyer and study poster. Screening will be conducted over the telephone and study information will be provided. Consenting and eligible participants will be sent an individualized link to the written consent form, written study information, and baseline

questionnaires. Those who pass the screening, including exercise safety, will be invited to an in-person physical assessment. Upon program completion, participants will be sent the questionnaires again (which also include the exit survey questions) and will attend a second in-person assessment of physical measures. Focus groups will be conducted to further assess the participants' perception of the study. If a participant has bilateral KOA, the most symptomatic knee will be studied. If both knees are equally affected, the dominant knee will be studied, which is the knee with which the individual steps first when initiating gait.

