#### **2.4. Randomization and blinding**

Participants will be randomized with an allocation ratio of 1:1 into one of two treatment groups (Pain Informed Movement or neuromuscular exercise and standard OA education) using a REDCap randomization module. The process of randomization will be conducted by a member of the research team who is independent of the recruitment process. Additionally, the assessors responsible for conducting baseline and follow-up assessments will be blinded and not involved in recruitment. Blinding of exercise instructors is generally not possible in studies of physical interventions (e.g., exercise) [21]. Participants will be blinded to study hypotheses and the two treatment groups. As both arms of the study are providing exercise-based interventions and education, participants will be provided limited details of each intervention arm so as to blind them from knowing which is the intervention and which is the control. This will help minimize any bias that occurs by knowledge of group assignment and perception of treatment effects.

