### **2.7. Primary and feasibility outcomes**

The primary outcome measure is the follow-up rate (i.e., number of participants that completed the program and attended follow-up). Other feasibility outcomes include: acceptability (content, format, frequency, and duration) of the Pain Informed Movement program compared to the control group, recruitment rate, burden of procedures, adherence rate (i.e., number of participants that attended all in-person sessions), compliance to the program (i.e., number of participants that reported completion of at least three exercise sessions per week), and AEs. A priori success criteria will be used to determine feasibility and acceptability of the programs (Table 2).

Table 2:

*A priori* feasibility criteria.

Outcome	A priori criteria		
	Proceed	Proceed with protocol amendments	Significant amendments required
Follow up	≥90% of participants followed up at 8 weeks	≥50% of participants followed up at 8 weeks	≤50% of participants followed up at 8 weeks
Recruitment	≥40 participants consent to participate/year	≥30 participants consent to participate/year	<30 participants consent to participate/year
Compliance to exercise program	≥80% of participants report exercise at least 3 times a week	≥50% of participants report exercise at least 3 times a week	<50% of participants report exercise at least 3 times a week
Program content acceptability – usefulness	≥50% found treatment useful (Likert ≥4/5)	≥25% found treatment useful (Likert ≥4/5)	<25% found treatment useful (Likert ≥4/5)
Program content acceptability – frequency	≥50% found frequency acceptable (Likert ≥4/5)	≥25% found frequency acceptable (Likert ≥4/5)	<25% found frequency acceptable (Likert ≥4/5)
Program content acceptability – duration	≥50% found duration acceptable (Likert ≥4/5)	≥25% found duration acceptable (Likert ≥4/5)	<25% found duration acceptable (Likert ≥4/5)
Format acceptability – delivery	≥50% found treatment delivery (in-person and home) acceptable (Likert ≥4/5)	≥25% found treatment delivery acceptable (Likert ≥4/5)	<25% found treatment delivery acceptable (Likert ≥4/5)
Adherence to in person treatment	≥75% of participants attended all in person treatment sessions	≥50% of participants attended all in person treatment sessions	≤25% of participants attended all in person treatment sessions

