## 2.11. Analysis

Descriptive statistics will be used to report feasibility outcomes. The quantitative analysis of secondary outcomes will be by intention-

to-treat principles. Repeated measures analysis of variance (ANOVA) will be used to assess the amount of change in outcome measures and compare them between the two groups using means and 95% CIs. Similarly, within group differences will be analyzed using the paired sample's t-test and will be reported using means and 95% CIs. Where possible we will also report minimally important difference.

The transcripts of the focus group interviews will be analyzed using thematic content analysis to identify suggestions for program modification [46]. Line-by-line reading of the transcripts will be performed and thematic patterns will be explored. Once themes and patterns are identified, each meaningful segment of text will be assigned a conceptual code.

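### With only two assessments, the planned repeated-measures ANOVA is an unadjusted change-score t-test; adjusting for the baseline value would usually narrow the intervals at almost no cost

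*Combined protocol and SAP*

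**What the plan says.** Section 2.11 (Analysis) covers the secondary outcomes in a few sentences. "Repeated measures analysis of variance (ANOVA) will be used to assess the amount of change in outcome measures" and to "compare them between the two groups using means and 95% CIs". Paired t-tests are added within each arm. Neither that section nor any other names a baseline covariate or an adjusted analysis.

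There are two measurement occasions. Under section 2.3, questionnaires are completed at baseline and sent again when the program ends, and participants "will attend a second in-person assessment of physical measures". Section 2.4 confirms the pair of visits: "the assessors responsible for conducting baseline and follow-up assessments will be blinded". Table 2 places follow-up at 8 weeks ("≥90% of participants followed up at 8 weeks").

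The between-arm comparison is exploratory (section 1.1, third objective), although the Introduction also says the trial will supply "initial efficacy data on the comparison of Pain Informed Movement program".

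**The concern.** With one baseline and one follow-up value per person, the repeated-measures model offers nothing beyond a comparison of mean change. Subtracting baseline fixes its coefficient at 1, whatever the actual relation between the two measurements. Estimating that coefficient from the data removes variance that the subtraction leaves in.

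At stake is the width of the between-arm intervals. With roughly 53 to 59 people followed up, those intervals largely determine what the pilot can say about efficacy to anyone designing the next trial. This is a matter of efficiency. No bias in the planned analysis has been demonstrated.

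**Working it through.** **Inputs from the documents.** 66 randomised 1:1 (sections 2.2 and 2.4). On retention, section 2.2 says "We will aim for 90% follow-up but will consider the trial successful if we achieve 81" per cent. 0.81 × 66 = 53.5, taken as 53 (26 and 27 per arm); 0.90 × 66 = 59.4, taken as 59. The plan states no precision or power for any secondary outcome, so there is no figure of its own to reproduce.

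**Assumed inputs.** r, the baseline to follow-up correlation: 0.3 to 0.9. k, baseline SD divided by follow-up SD: 0.8, 1 and 1.25. All results are in follow-up SDs.

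**Step 1: equivalence.** On one simulated data set with 30 per arm, the group-by-time F was 0.79788 and the squared t for change was 0.79788 (p = 0.3754 for both). They are the same test.

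**Step 2: large-sample variances.**
- Change score: 1 + k² − 2rk.
- Baseline-adjusted regression (ANCOVA): 1 − r².
- Difference: (k − r)². This is never negative, and is zero only when k = r.

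Reduction in standard error = 1 − √[(1 − r²)/(1 + k² − 2rk)]:

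| k | r = 0.3 | r = 0.5 | r = 0.7 | r = 0.9 |
|---|---|---|---|---|
| 0.8 | 11.4% | 5.5% | 1.0% | 2.5% |
| 1 | 19.4% | 13.4% | 7.8% | 2.5% |
| 1.25 | 29.1% | 24.4% | 20.8% | 22.0% |

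**Step 3: 95% interval half-widths at the trial's size.** These use t quantiles on N − 2 df (change) and N − 3 df (ANCOVA), and multiply the ANCOVA variance by 1 + 1/(N − 4) for estimating the slope. Example for N = 53, r = 0.5, k = 1, with √(1/26 + 1/27) = 0.2748:
- Change: 2.0076 × 0.2748 × √1 = 0.552.
- ANCOVA: 2.0086 × 0.2748 × √(0.75 × 1.0204) = 0.483.

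| N = 53 | r = 0.3 | r = 0.5 | r = 0.7 | r = 0.9 |
|---|---|---|---|---|
| ANCOVA | 0.532 | 0.483 | 0.398 | 0.243 |
| Change, k = 0.8 | 0.594 | 0.506 | 0.398 | 0.247 |
| Change, k = 1 | 0.653 | 0.552 | 0.427 | 0.247 |
| Change, k = 1.25 | 0.743 | 0.632 | 0.497 | 0.308 |

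For N = 59 and r = 0.5, the half-width is 0.478, 0.521 or 0.597 for change (k = 0.8, 1, 1.25) against 0.456 for ANCOVA. In the least favourable case, k = r, the ANCOVA interval is 1.06% wider at N = 53 and 0.94% wider at N = 59.

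**Step 4: validity of both.** In simulations at N = 53 (no true effect, no informative drop-out, 20,000 replicates for each of the 12 r-by-k combinations), coverage was 94.8% to 95.1% for the change score and 94.7% to 95.3% for ANCOVA.

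**Step 5: drop-out.** Illustrated at r = 0.5 with 81% retained and informative drop-out in one arm only, at an odds ratio of 2 per SD.
- If drop-out depends on baseline, completers' mean baseline shifts by −0.1226 SD. The change score is biased by (r − k) × (−0.1226) = 0.037, 0.061 or 0.092 SD at k = 0.8, 1, 1.25; ANCOVA by 0.002 or less.
- If it depends on the unseen follow-up value, the absolute bias is 0.075, 0.062 or 0.047 SD for the change score and 0.092 to 0.095 SD for ANCOVA.

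The documents do not say which pattern to expect, so drop-out favours neither method.

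**The case against.** The strongest case on the other side is that the planned analysis is already sound, the outcomes are exploratory, and the gain is assumed. All three points are true and limit how much this matters.

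The gain may also be smallest where interest is greatest. Table 1 requires "Having an average pain intensity of at least 3/10 on a numeric pain scale on most days of the past month", which may compress baseline pain and make k less than 1. At N = 53 and k = 0.8, the ANCOVA interval is 4.5% narrower at r = 0.5 and no narrower at r = 0.7. At k = r = 0.7 it is 1.1% wider. The largest gains need k = 1.25, which nothing in the documents supports for any outcome. So the benefit for pain intensity may be slight. Scales such as the PCS, HADS, KOOS and sit-to-stand have no entry threshold of their own, so the same argument does not apply to them directly.

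Three conditions also deserve stating. Both arms are taught in groups, and the coverage results assume independent participants; correlation within classes would affect either analysis, so it does not decide between them. Baseline must be unaffected by allocation. The order described (baseline assessment by blinded assessors, before the intervention) fits this, although the moment of randomisation is not given. Finally, ANCOVA does not resolve missing 8-week values under intention to treat.

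None of this removes the central asymmetry: a possible loss of about 1% in interval width against a gain that is often several times larger.

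**Conclusion.** The concern holds. The between-arm comparison in section 2.11 is an unadjusted change-score t-test, and the baseline value that would sharpen it is already collected. At r = 0.5 and N = 53, adjustment reduces the half-width from 0.51, 0.55 or 0.63 SD (k = 0.8, 1, 1.25) to 0.48 SD. Over the whole assumed range the result runs from a tie to an interval about 28% narrower (0.743 to 0.532), with a worst case of about 1% wider when k equals r. These sizes rest on assumed r and k, independent participants and a roughly linear relation to baseline with a common slope. The change should be made because it is nearly free. It does not affect the primary outcome, the Table 2 criteria or the sample size.

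**What to change.** In section 2.11, replace the repeated-measures ANOVA for each continuous secondary outcome with a linear regression of the 8-week value on randomised arm and the baseline value of that outcome. Keep participants in their randomised arm, and report the adjusted mean difference with its 95% interval. Change can still be presented: with change as the response and baseline as covariate, the arm effect is identical. Temporal summation, scored present or absent in Table 3, falls outside this recommendation.

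The cost is one or two sentences, one line of code per outcome and one degree of freedom. If outcome data have already been examined by arm, the change should be recorded as post hoc.
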